10.2 Informed consent

Informed consent will be sought from potential participants using information sheets and consent forms available in relevant languages. Written informed consent will be sought, with the assistance of a translator or a witness where necessary, using standard consent forms. In occasions where the participant is not able to undergo the informed consent process (mental retardation, altered level of consciousness, somnolence, obtundation, stupor or certain psychiatric conditions) an authorized relative might provide the written consent as a witness. In the case these conditions are temporal, patients would be reconsented when they are in full capacity. Participants unable to read or write will be asked to make a mark or thumbprint in the presence of a witness. Details on standard informed consent procedures will be specified in site standard operating guidelines. The ICF will include a section to access to medical records and collection of relevant data from them.

10.3 Assessment for eligibility

All inclusion/exclusion criteria must be assessed among those HIV-positive patients admitted in the ward and who have signed the informed consent.

For those patients who are not eligible, study staff will inform them that they will not be able to participate in the study and will receive the local standard of care.

10.4 Recruitment

A participant is considered recruited for the study when the participant has signed the informed consent, meets all the inclusion criteria and does not fulfill any of the exclusion criteria.

For those patients enrolled in the study, all the screening procedures will be documented in the screening logs and appropriate case report forms (CRFs) will be completed before starting the procedures specific to the control or intervention arm, including:

- a) Basic socio-demographic information
- b) Relevant medical history
- c) Physical exam

Basic sociodemographic information and relevant medical history will be collected from the

This project is part of the EDCTP2 programme supported by the European Union

participant/caregiver or, if available, from existing medical records. A locator form (as a source document) will include contact information of the participant and/or caregiver or relative (with at least one mobile phone number to reach out the participant after discharge).

Time from admission (as recorded in medical history) to study enrolment will be recorded. However, this time should be as short as possible, preferably less than 12-24 hours.

10.5 Randomization

This is an individually randomized clinical trial. Eligible participants will be randomized to either the intervention or control arm, with an expected 50% of participants allocated to each of the arms. Randomization will be conducted using a web-based application (Enketo software) that can be used in any smartphone device or computer with internet connection. The day of randomization for each participant will be the enrolment day (study Day 0). At the time a participant is randomized, the study staff enters in the application several key data (patient study number and date of birth) and in reply, the randomization arm is provided a few seconds later in the same application interface. Thus, internet connection is needed for randomizing participants. Pre-registered users of the study team will be allowed to use the randomization application.

Developing a reliable training plan by which study teams (at the clinic and at the lab) are fully aware of the diagnostic allocation is critical so that arm-specific testing can be implemented without mistakes in a timely manner. This includes careful strategic measures (posters, signs, weekly meetings, etc) as part of the site internal planning, which also need to consider staff shifts, holidays (both in the hospital and at the laboratory). A screening and randomization log need to be daily updated. Day 0 CRF needs to be data entered in a timely manner to allow the central monitoring of number of recruited subjects per arm, site and week and overall mapping of participants included in the study.

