- We estimate the increased yield of Ultra in urine and stool as if this additionality were independent, considering that this yield would come from potentially different phenotypes of TB patients. Otherwise, some of the gain observed by Urine Xpert Ultra or Stool Xpert Ultra might overlap and thus we could be overestimating the expected additionality in bacteriological confirmation in these samples.
- We obtained the Xpert Ultra added yield from studies performed in TB presumptive HIV positive inpatients and outpatients. Estimates of added yield vary widely in the literature. However, given that major gain of Xpert Ultra has been observed in HIV positive patients and smear negative patients, we think that the added yield of Ultra in our population (strictly admitted PLHIV) could be higher, and potentially greater in extrapulmonary samples such as stool or urine (as a recent study -Kabir et al, 2021 -of Stool Ultra in children

This project is part of the EDCTP2 programme supported by the European Union

has shown). In this regard, we have taken a conservative approach by using the reference of Dorman et al, 2018.

- The added yield of Ultra over Xpert does not consider that some of that additional yield might be picked up by Urine AlereLAM (optimistic approach).
- Some of these limitations may impact both the control and the intervention arm and thus would probably have a limited effect on our expected difference in bacteriologically confirmed cases that we aim to detect through this study.

Assuming that we will find 19% of bacteriologically confirmed cases in the control arm following the WHO indications for sputum Xpert® Ultra and AlereLAM in HIV hospitalized patients (based on previously mentioned data), and a two-sided type I error of 5%, the inclusion of patients per arm would provide an 80% power to detect a 7% increase in the percentage of bacteriologically confirmed TB diagnosis allowing for a loss to follow-up of 5%.

Based on these estimates, the study will require a total of 586 PLHIV participants to be enrolled per trial arm. For both arms together, this yields 1172 patients in total.

Given that 4 sites will be recruiting patients, this means approximately 293 participants per site (around 147 per arm at each site).

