## 4.3 Randomisation and Blinding

This is an individually randomized clinical trial. Eligible participants will be randomized to either the intervention or control arm, with 50% of participants in each of the arms. Randomization will be conducted using a web-based application <https://odk-central.finddx.org/-/x/6RPyVJQoEjzOPUd3qHIRQYX6MtFnnwq> that can be used on any smartphone device with internet connection. The day of randomization for each participant will be the enrolment day (study Day 0). At the time a participant is randomized, the study staff enters in the application several key data (patient study number and date of birth) and in reply, the allocated randomized arm is provided a few seconds later in the same application interface. Thus, internet connection is needed for randomizing participants. Pre-registered users of the study team will be allowed to use the randomization application.

Developing a reliable training plan by which study teams (at the clinic and at the lab) are fully aware of the diagnostic allocation is critical so that arm-specific testing can be implemented without mistakes in a timely manner. This includes careful strategic measures (posters, signs, weekly meetings, etc) as part of the site internal planning, which also need to consider staff shifts, holidays (both in the hospital and at the laboratory). A screening and randomization log need to be daily updated. Day 0 CRF needs to be data entered in a timely manner to allow the central monitoring of number of recruited subjects per arm, site and week and overall mapping of participants included in the study.

This is an unblinded trial. Neither participants, nor study staff will be blinded to tests practiced or test results.

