## 5 Sample Size

We expect the absolute difference in proportions of bacteriological confirmation between the two arms to be 7% (from 19% to 26% from the control to the intervention arm). Sample size was chosen to be sufficient to detect a 36.8% relative increase in the primary outcome in the intervention arm (as compared to the control arm).

Under this premise and the following assumptions:

- Alpha (two sided): 0.05
- Beta (power 80%): 0.2
- Estimated proportions of participants with microbiologically confirmed TB in the control arm 19% and in the intervention arm 26%
- Lost to follow up: 5% of recruited participants.

The study will recruit 586 PLHIV participants per trial arm, then we will include in the analysis 1172 participants in total. This number of participants will come from 4 sites (293 participants per arm at each site).

For this calculation we have used the following formulas based on Normal asymptotic approximation for proportions:

Sample Size formula

$$n_1 = \frac{\left( Z_{1-\alpha/2} \sqrt{(1 + \varphi) \bar{p}_1 (1 - \bar{p}_1)} + Z_{1-\beta} \sqrt{\varphi p_1 (1 - p_1) + p_1 (1 - p_1)} \right)^2}{\varphi |p_1 - \bar{p}_1|^2}$$

Power formula

$$\varphi = \frac{1 - w_1}{w_1}$$

$$\bar{p} = \frac{p_1 + \varphi p_2}{1 + \varphi}$$

$$1 - \beta = \Phi \left( \frac{|p_1 - \bar{p}| \sqrt{\varphi w_1} - Z_{1-\alpha/2} \sqrt{(1 + \varphi) \bar{p} (1 - \bar{p})}}{\sqrt{\varphi p_1 (1 - p_1) + p_2 (1 - p_2)}} \right)$$

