### 6.3 Multiple Testing

We consider unnecessary to apply a general adjustment of significance level by multiple comparisons test. We will use the all the statistical power for inference only in the primary study objective. To evaluate the other study endpoints, we use the p-value threshold at 0.05 to find the differences in our study without the objective to extrapolate the results to the global community. However, we will establish a p-value of 0.01 as a threshold for statistical significance in the comparisons related to a) selected secondary efficacy analyses (section 8.2, analyses 8.2.5, 8.2.6, 8.2.7) and subgroup analysis (see section 9.0)

We will adjust the results by site, demographic variables, and other baseline variables if we will detect differences or if these variables have a confounder characteristics profile. To decide this, we will do a preliminary analysis of these variables between sites.

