## 9. Subgroup analysis

The analysis of all endpoints will be done for all patients of both countries as sample size did not take into consideration country-specific analyses of the specified primary endpoint. Thus, we will merge the data from the four sites we will analyse the resulting database as unique source of data.

However, a subgroup analysis of the primary endpoint and main secondary endpoint (mortality at month 2) will be done by study site (Mozambique and Tanzania, CD4 counts and viral load).

A separate analysis of the primary and secondary endpoints will also be performed by sex of participants, in order to assess if differences arise in any of the outcomes.

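### The allocation method is not stated and site enters the primary analysis only conditionally: a small, avoidable loss of precision and an open choice of primary result

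*Protocol*

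**What the plan says.** **Allocation.** Protocol 10.5: "Eligible participants will be randomized to either the intervention or control arm, with an expected 50% of participants allocated to each of the arms". The inputs named in both documents are few. In SAP 4.3, "the study staff enters in the application several key data (patient study number and date of birth" are what is entered before the arm is returned. Neither section mentions blocks, strata or minimisation, and neither says that allocation is unrestricted. Protocol 13.1 nevertheless plans on "around 147 per arm at each site" without saying what would deliver that balance.

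**Primary analysis.** SAP 8.1 specifies a two-sample z test on the difference in proportions, with no site term. SAP 9 adds that "we will merge the data from the four sites we will analyse the resulting database as unique source of data".

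**Where site or country appears.**
- SAP 6.3: "We will adjust the results by site, demographic variables, and other baseline variables if we will detect differences", or if the variables look like confounders. A preliminary between-site analysis of these variables decides. No threshold, model or estimator is given.
- SAP 8.1: the risk difference is to be stratified by country and baseline CD4. No rule is given for combining the strata, and it is not said whether a combined figure would be primary.
- SAP 9: a subgroup analysis by study site, which the text then explains as the two countries.
- SAP 8.2.7: site is a covariate in the models for time to TB diagnosis, a secondary endpoint.
- Protocol 13.2.2: heterogeneity between sites will be examined, and adjustment for country or hospital is possible, with detail left to the analysis plan.

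**The concern.** Four sites in two countries may well differ in how often the primary endpoint occurs. If so, an unadjusted comparison has two small weaknesses. Under simple allocation, chance differences in site mix between arms add noise that a site-stratified estimate would remove. Under site-stratified allocation, the pooled standard error ignores the strata and is too wide.

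The second matter is which result is primary. SAP 6.3 makes site adjustment depend on the data without defining the trigger, and SAP 8.1 mentions a stratification without an estimator. A reader cannot tell in advance which estimate and p-value will be reported as primary. The trial is unblinded (Protocol 10.6), so an unambiguous primary analysis is worth having.

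**Working it through.** **Inputs from the documents.** SAP 5 gives a two-sided 5% level, 80% power, rates of 19% (control) and 26% (intervention), and 5% loss. Protocol 13.1: 586 per arm, 1172 in total, four sites of about 293. (SAP 5 gives 293 per arm at each site, which would total 2344; only the protocol's version agrees with 1172.)

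**Assumed.** Neither document gives endpoint rates by site, so the between-site SD is varied from about 3 to 12 points.

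**1. The plan's sample size.** With the pooled variance and a mean rate of 0.225:

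n = [1.96 × √(2 × 0.225 × 0.775) + 0.8416 × √(0.19 × 0.81 + 0.26 × 0.74)]² / 0.07² = (1.1575 + 0.4953)² / 0.0049 ≈ 558.

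558 × 1.05 = 586, the stated figure.

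**2. Unadjusted precision at 586 per arm.** SE = √[(0.1539 + 0.1924)/586] = 2.43 points. Power = Φ(7/2.43 − 1.96) = 82.1%.

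**3. Balance within a site if allocation is simple.** For a site of 293, the 95% range of the number in one arm is 146.5 ± 1.96 × √293/2, about 130 to 163.

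**4. Shift from chance site mix if allocation is simple.** SD of shift ≈ 2 × SD_between/√1172. For SD_between = 6.7 points, 2 × 6.7/34.23 = 0.39.

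**5. Gain from stratifying.** The share of variance removed is SD_between² divided by the mean of p(1−p), which is (0.1539 + 0.1924)/2 = 0.173. For 6.7 points, 0.0045/0.173 = 2.6%.

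The shift and type I error columns below are simulated (four sites of 293). Stratified power is from the formula at 586 per arm, against 82.1% unadjusted.

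| Assumed control rates (%) | Between-site SD (points) | SD of shift (points) | 95% limit (points) | Variance removed | Stratified power | Type I error, pooled test, if allocation is site-stratified |
|---|---|---|---|---|---|---|
| 14.5, 17.5, 20.5, 23.5 | 3.4 | 0.20 | 0.38 | 0.6% | 82.4% | 4.9% |
| 14, 14, 24, 24 | 5.0 | 0.29 | 0.58 | 1.4% | 82.7% | 4.9% |
| 10, 16, 22, 28 | 6.7 | 0.39 | 0.77 | 2.6% | 83.1% | 4.7% |
| 9, 9, 29, 29 | 10.0 | 0.59 | 1.16 | 5.8% | 84.3% | 4.4% |
| 4, 14, 24, 34 | 11.2 | 0.65 | 1.28 | 7.2% | 84.8% | 4.2% |

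At an SD of 12 points the formula gives 2 × 12/34.23 = 0.70, with a 95% limit of 1.4 points.

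**6. Validity.** Under simple allocation the pooled test kept its type I error at 4.95% to 5.06% in every scenario. The site-mix variation is already inside the 2.43-point SE.

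**7. Worst case of the open choice.** Under simple allocation and no effect, the pooled and the stratified test each hold about 5%. If significance on either could be claimed, the error is about 5.2% to 6.3% over the same range of site SDs. With a true 7-point effect, the two tests disagree on significance in about 3% to 6% of trials at site SDs from about 7 to 12 points.

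**The case against.** The case for leaving the plan alone is substantial.

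- *The pooled test is not invalid.* This stands. Under simple allocation it holds its level; under stratified allocation it errs on the safe side.
- *The gain is small.* This stands. Up to a site SD of 6.7 points, power rises by at most 1 point; gains of 2 to 3 points need SDs of 10 or more.
- *Site and country are not ignored.* True, as the list of places above shows. None of them, however, fixes one site-adjusted estimator for the primary endpoint.
- *The trigger in SAP 6.3 is a preliminary look at covariates, not at both primary results.* This stands as a matter of wording, and nothing suggests that the team means to pick a result. The 5.2% to 6.3% therefore bounds what the undefined rule allows; it does not predict conduct.

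Three stronger readings are tempting and are not supported.

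- A reader might infer that allocation is simple. The documents are silent: site could be carried by the study number or the user login, and the planned 147 per arm at each site fits stratification at least as well.
- A reader might infer a bias of about 1 point in the primary difference. That size is a 95% limit, reached only when the between-site SD is about 8.7 points, and it is random error, not bias. Protocol Table 1 (HIV-positive TB incidence 101 versus 47 per 100 000) does not establish such differences, because those are national population figures and all participants are HIV-positive inpatients. If rates around 22.5% did follow that ratio (30.7% and 14.3%, SD 8.2), the shift would have an SD of 0.48 and a 95% limit of 0.94 points.
- A reader might infer that allocation must be changed. Once site is in the analysis, simple allocation costs about 1/293, or 0.3%, in efficiency, and blocking by site makes assignments more predictable in an open-label trial.

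**Conclusion.** The point holds as a minor one. The documents do not state how allocation is done, the primary test is unadjusted on merged data, and whether site is adjusted for depends on an undefined preliminary analysis.

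The pooled test is valid if allocation is simple, but it gives up about 0.1 to 3 power points at 586 per arm, with a chance shift of SD about 0.2 to 0.7 points (95% limit about 0.4 to 1.4) against a planned 7. If allocation is stratified by site, the pooled test is mildly conservative, at about 4.1% to 4.9%. These sizes rest on assumed between-site SDs of about 3 to 12 points, equal sites and a common risk difference; with no site differences they vanish.

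The better reason to act is clarity: a site-stratified primary analysis suits either allocation method and settles which result is primary.

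**What to change.** Before database lock:

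1. **SAP 8.1.** Make the primary estimate the Mantel-Haenszel risk difference stratified by the four sites, with the matching stratified test. Keep the unadjusted difference as a sensitivity analysis. Say that the country and CD4 breakdown is descriptive or subgroup material, not a competing primary estimate.
2. **SAP 6.3.** Remove site from the conditional adjustment rule.
3. **SAP 4.4 and 9.** Define site as the four recruiting institutions and name the variable. SAP 4.4 lists country but no site variable, and SAP 9 uses site for the two countries.
4. **Protocol 10.5 and SAP 4.3.** State the allocation method actually used, including any blocks or strata.

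The cost is wording only: no extra participants, no new data collection and no change to the allocation method.

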10.6 Blinding

This is an unblinded trial. Neither participants, nor study staff will be blinded to tests practiced or test results.

Enrolment and testing will be done by study staff. AlereLAM will be done at the hospital or at a short distance from hospital (for example, same building hospital laboratory). Results of all tests will be provided to routine clinical staff who will make decisions on treatment initiation.

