| Control arm | 
The control arm for this trial will consist of patients managed according to the current WHO recommended TB testing practices for HIV positive inpatients (as of Q1 2020). TB testing will be done as follows:
 
Sputum Ultra performed whenever the patient has cough, fever, weight loss over night sweats and/or
 
Ultra performed on any tissue (including lymph nodes) from patients with clinical suspicion of extrapulmonary TB.
 
and/or:
 
Urine Alere TB-LAM performed if patients have signs and symptoms of TB (pulmonary and/or extrapulmonary), or with advanced HIV disease, or who are seriously ill, or else irrespective of signs and symptoms of TB, but combined with a CD4 cell count of less than 200 cells/mm³.
 |
| Study Population and Sample Size | 
Our study population will be adult HIV-positive patients admitted to hospital and living in the catchment areas within the 4 participating district hospitals in Tanzania and Mozambique, regardless of presence of TB attributable symptoms.
 
Sample size was chosen to be sufficient to detect a 36.8% relative increase in the primary endpoint in the intervention arm (as compared to the control arm).
 
Calculations were based on following assumptions:
 
 - Alpha: 0.05 - Beta: 0.2 (power=80%) |

| | |
|-------------------------------------|---|
| | 
 - Estimated proportion of participants with microbiologically confirmed TB in the control arm: 19% - Estimated proportion of participants with microbiologically confirmed TB in the intervention arm: 26% - Lost to follow up rate for primary endpoint: 5% of recruited participants. 
Based on these estimates, the study will require a total of 586 HIV participants to be enrolled per trial arm. For both arms together, this amounts to 1172 patients in total (293 per site).
 |

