C-reactive protein (CRP) indicates inflammation and can be detected on capillary blood. WHO has recently recommended CRP as a method for TB screening among ambulant people living with HIV who are newly in care and not yet on antiretroviral treatment, based on similar sensitivity and specificity to symptom screening in HIV-positive populations⁴¹.

LumiraDx

LumiraDx is a recently developed point-of-care instrument that is currently available for SARS-CoV-2 testing in anterior nasal specimen, Dimer-D and CRP quantification in venous blood (<https://www.lumiradx.com/us-en/what-we-do/diagnostics/test-technology/>). While its use has not yet been tested for TB, the company is developing a *Mtb* kit to be tested in tongue swabs. LumiraDx is a fast (10min) and easy-to-use device, with potential for adding innovative POC solutions to TB diagnosis.

This project is part of the EDCTP2 programme supported by the European Union

6. Aim and hypothesis

The overall aim of this study is to assess the potential of an expanded TB testing strategy to increase the number of HIV-positive patients with microbiologically diagnosed TB who are started on treatment in adult wards of sub-Saharan Africa.

Previous studies have shown that Xpert testing of urine and stool are capable of confirming *Mtb* in patients who would otherwise test negative with traditional sputum-based methods. Evidence shows that these diagnostics may detect additional cases that are not detected by AlereLAM. Thus, an algorithm using the different tests (sputum Ultra, urine Ultra and stool Ultra) offered as a screening intervention to admitted HIV positive patients should increase the *Mtb* bacteriological yield (compared to current WHO recommended screening and testing strategies**) and contribute to earlier initiation of TB treatment. Given that some detected cases may not present with classical TB symptoms at the time of hospitalization, we believe that this strategy will increase the overall number of patients with diagnosed TB and started on treatment and ultimately reducing mortality.

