8.3 Exploratory endpoints

- Diagnostic performance of a molecular TB diagnostic assay (Xpert Ultra and/or LumiraDx) on tongue swabs, and FujiLAM on urine against a microbiological reference standard (as defined in intervention arm) or against a composite reference standard that includes bacteriologically confirmation or/and clinical evidence resulting in therapy initiation. This endpoint will only be studied in participants of the intervention arm
- Diagnostic accuracy of CRP in blood in order to evaluate compared to TB symptom's screening in those with microbiologically confirmed TB.
- Comparison of primary and secondary endpoints of the intervention arm with the local standard of care at the sites before the study initiation (a retrospective data collection from consecutive HIV-positive patients admitted at participating hospitals).

This project is part of the EDCTP2 programme supported by the European Union

9. Trial Design and study arms

This is a multicentre, parallel, individually randomized controlled diagnostic trial in consecutively enrolled HIV positive adults to evaluate the impact of the extended use of Xpert Ultra (3 specimens) for TB diagnosis, using sputum, stool and urine, AlereLAM among consecutive PLHIV admitted to hospitals in 4 sites of 2 high burden African countries (Tanzania and Mozambique). Thus, the **intervention arm** for this trial will include TB testing performed irrespective of the presence of TB symptoms. Testing will be done on expectorated sputum, stool and urine with Ultra and urine with AlereLAM.

To fulfil exploratory objectives, we will also collect 2x tongue swabs for molecular TB diagnostic assay (Xpert Ultra and/or LumiraDx) testing, blood for CRP, and urine samples which will be stored for retrospective FujiLAM testing and analysis.

The **control arm** for this trial consist of patients managed according current WHO testing recommendations (as of Q1 2020) for HIV-positive inpatients. TB testing will be done as follows:

- a) ***Sputum Ultra*** whenever the patient has cough, fever, weight loss or night sweats and/or Ultra performed on any tissue (including lymph nodes) in patients with clinical suspicion of extrapulmonary TB.
and/or
- b) ***Urine Alere TB-LAM***, if patients have signs and symptoms of TB (pulmonary and/or extrapulmonary), or with advanced HIV disease or who are seriously ill or else irrespective of signs and symptoms of TB and with a CD4 cell count of less than 200 cells/mm³.

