9.3 Sample size

In order to detect a 36.8% relative difference (26% vs. 19%) in the proportion of admitted PLHIV who are bacteriologically confirmed TB positive between the intervention and control arm, the study will require a total of 586 participants to be enrolled per trial arm, whereby drop-out rates are considered (details see below). For both arms together, this yields 1172 patients in total. Given that 4 sites will be recruiting patients, this represents a mean of 293 participants per site (147 per arm at each site). Further details on sample size estimation can be found in (statistical considerations).

10. Study procedures

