10.7 Minimisation of Error and Bias

Selection bias will be minimized by a) the randomization process and b) consecutive enrolment of participants meeting inclusion criteria (and not meeting exclusion criteria). Study staff from all sites will be trained prior to study initiation in order to guarantee that inclusion and exclusion criteria and

This project is part of the EDCTP2 programme supported by the European Union

well understood and applied homogenously across sites.

Other potential sources of bias (ascertainment, information, interpretation), will be also addressed. Laboratory procedures will be standardized across sites, using the same laboratory SOPs and specific lab training, in order to minimize differences by site. Given that most tests are different by arm, and that AlereLAM will be preferably done at the health facility (by the bed side), no blinding of attending physician or lab technologist will be possible. In order to explore the differences between WHO recommended procedures and real standard of care at the sites, there is an exploratory objective aiming at assessing the current yield of TB investigations under routine conditions prior to the study initiation at all sites. This will be consecutive collection of retrospective data from PLHIV admitted at participating hospitals prior the start of the study. The quality and completeness of this data might differ from participating sites.

Decision to start TB treatment will be based on any test results and the criteria of the physician responsible for the patient's care.

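### CRP is listed for the intervention arm only and nothing keeps its result from treating staff, so the 72-hour treatment-timing part of the primary endpoint cannot be cleanly attributed to the expanded TB testing

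*Protocol*

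**What the plan says.** **The strategy.** Protocol Section 7 defines the expanded strategy as Ultra on sputum, urine and stool plus urine AlereLAM. CRP is not in it. Section 9 adds CRP for exploratory purposes, after the tongue swabs: "blood for CRP, and urine samples which will be stored for retrospective FujiLAM testing and analysis". Protocol Table 2 (Section 11) and the SAP schedule (4.1) both put CRP blood in the intervention column at Day 0 and not in the control column.

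**Who sees results.** The trial is unblinded. Protocol 10.6: "Results of all tests will be provided to routine clinical staff who will make decisions on treatment initiation". Protocol 10.7: "Decision to start TB treatment will be based on any test results and the criteria of the physician responsible for the patient's care". Section 10.10 adds that study and routine staff decide jointly. None of these makes an exception for CRP.

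**When tests are run.** FujiLAM is done retrospectively on banked urine (12.2.2), and tongue swabs are stored for later testing (12.1.4, 12.5.3). CRP has no equivalent statement, and the indications conflict:
- The synopsis lists CRP blood in a sentence about collecting and storing material, which points to later testing.
- Section 12.5 gives storage steps for urine and swabs but none for blood.
- CRP shares a case report form with AlereLAM, which is read on site (Protocol 14.2, SAP 4.4).
- Section 12.3 describes putting a blood specimen on the LumiraDx device, with a result in 10 minutes.

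**The endpoint.** A primary success needs a positive Ultra or AlereLAM and treatment within 72 hours of enrolment. Confirmation may arrive after 72 hours if treatment had already begun (Protocol 8.1 and 13.2.2).

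**The concern.** Treatment within 72 hours is half of the primary endpoint. If CRP is read on Day 0 and released, clinicians in one arm hold an extra signal that is not part of the declared strategy. The protocol itself presents CRP as a TB screening tool: "WHO has recently recommended CRP as a method for TB screening among ambulant people living with HIV" (Section 5.3). A raised value could prompt an empirical start while Ultra is pending or a specimen has yet to be produced. If confirmation follows, that participant counts as a success.

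The route is open under the protocol's own timings. Specimens may be collected up to 72 hours after enrolment or later (10.9.1, 10.9.2), and Ultra results are due within 24 hours of collection (Section 12). Some confirmatory results can therefore arrive after the window closes.

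At stake is attribution: part of the difference between arms could come from a co-intervention that the conclusion would not mention. The secondary endpoint of any TB treated within 72 hours needs no confirmation, so a start prompted by CRP counts there directly. Eight-week mortality could also be touched. The SAP variable list (4.4) records reasons for not starting within 72 hours, but not what prompted a start. It has no CRP variable, and Section 8.1 plans no analysis that would isolate the effect.

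**Working it through.** **1. The plan's own figure.** Inputs are 19% versus 26%, two-sided 5%, 80% power, 1:1 allocation and 5% loss (Protocol 10.5 and 13.1, SAP 5). With p̄ = 0.225:

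n = [1.960 × √(2 × 0.225 × 0.775) + 0.842 × √(0.19 × 0.81 + 0.26 × 0.74)]² / 0.07² = 558 per arm.

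Multiplying by 1.05 gives 586, as stated. Dividing by 0.95 gives 588. The figure reproduces and is not in dispute. Power at 557 evaluable per arm is 80.0%.

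**2. What CRP could add to the primary endpoint.** Notation:
- m = 26%, the planned confirmed proportion in the intervention arm (Protocol 13.1).
- s = share of confirmed cases that would start within 72 hours without CRP, taken as equal in both arms. The documents do not give it; it is assumed.
- f = share of the otherwise late confirmed cases that CRP moves inside 72 hours. This is also assumed.

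CRP contribution = m × (1 − s) × f.

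| Late (1 − s) | Moved (f) | Contribution (points) |
|---|---|---|
| 10% | 5% | 26 × 0.10 × 0.05 = 0.13 |
| 10% | 50% | 26 × 0.10 × 0.50 = 1.3 |
| 20% | 5% | 26 × 0.20 × 0.05 = 0.26 |
| 20% | 50% | 26 × 0.20 × 0.50 = 2.6 |

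If CRP is tested later or not released, f = 0 and so is the contribution.

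**3. Set against the gain from testing.** The part due to extra yield is 7 × s. With f held at 25%:

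| s | From testing | From CRP | Total | CRP share |
|---|---|---|---|---|
| 0.95 | 6.65 | 0.3 | 7.0 | 5% |
| 0.90 | 6.3 | 0.65 | 6.95 | 9% |
| 0.80 | 5.6 | 1.3 | 6.9 | 19% |
| 0.60 | 4.2 | 2.6 | 6.8 | 38% |

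The last row lies outside the range in step 2. It shows how the share grows when many starts are late.

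**4. If testing added no yield.** Take 19% confirmed in both arms, s = 0.80 and f = 0.25. The proportions are 19 × 0.80 = 15.2% in control and 19 × (0.80 + 0.20 × 0.25) = 16.15% in intervention, a shift of 0.95 points. At 557 per arm the chance of a significant result favouring the intervention is 6.4%, against a nominal 2.5%. At s = 0.95 it is 3.2%.

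**The case against.** A reader might infer that the effect cannot be credited to the expanded testing at all. The documents do not support that. The numerator needs a positive Ultra or AlereLAM. Every intervention participant is already due all of these tests, so CRP does not trigger them. It acts only on confirmed cases that would otherwise start late. Confirmed TB by arm (SAP Tables 2 and 4) is largely free of this route, and SAP Table 3 splits 72-hour starts by confirmation.

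A reader might also take bedside CRP as established. It is a fair inference, but it is not stated. The synopsis points the other way, and the numbering in 12.5 skips 12.5.2, so absence from that list is weak evidence. A shared form shows where a result is recorded, not when the test is run. The reference to all tests in 10.6 cannot be fully literal either, because FujiLAM and swabs are tested later.

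The mechanism may be weak. Section 5.3 limits the CRP recommendation to ambulant people newly in care and not yet on antiretroviral treatment, and says CRP performs much like symptom screening. Symptom screening is done in both arms at Day 0, so CRP may add little to what clinicians already know. Late starts caused by logistics would not respond to CRP.

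These arguments stand, and they lower the plausible value of f. They do not close the route: no passage withholds CRP, and the contrast with the explicit handling of FujiLAM and swabs remains.

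**Conclusion.** The point holds as a problem of attribution, confined to treatment timing. Followed as written, and if CRP is run on the day, the plan contains an undeclared one-arm co-intervention on that part of the primary endpoint. It does not undermine the yield part.

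The size is unknown. It runs from about 0.1 points (10% late, 5% moved by CRP) to 2.6 points (20% late, 50% moved), against a planned difference of 7. Both inputs are assumptions, and the effect is nil if CRP is not released. Any TB treated within 72 hours is more exposed because it has no confirmation requirement. An effect on mortality is possible, but the documents give no basis for an estimate. The change is worth making because it is cheap and the ambiguity is real.

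**What to change.** 1. Reconcile the Protocol synopsis, Sections 9, 10.6, 10.7, 12.5 and 14.2, and Table 2 on when CRP is run and in which arm. Section 14.2 heads its form list as for all participants, although CRP is scheduled in one arm.
2. Then do one of the following:
   - Except CRP from the results released under 10.6, withholding it from treating staff at least until the participant's 72-hour window closes, or until week 8 if the mortality comparison is also to be protected. Withholding does not by itself require stored blood.
   - Declare CRP part of the intervention in the arm definition, the primary objective and the conclusion.
3. Add to SAP 8.1 a sensitivity analysis of the primary endpoint that counts, in both arms, only treatment starts at or after a positive Ultra or AlereLAM result. SAP 4.4 already lists treatment date and time, and result date and time for sputum Ultra, urine Ultra and AlereLAM. It lists no result time for stool Ultra, so that must be added; the same gap applies to Ultra on other specimens. This analysis also drops empirical starts that Protocol 8.1 counts on purpose, so it belongs beside the primary analysis and does not replace it.

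The cost is short protocol wording and a little more analysis. If CRP is withheld, clinicians do not have it in real time.
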